6.3.1 Data Submission

The site will complete and submit the following case report forms and device print outs to Abbott Medical using the EDC system:

- System Revision Form
- Device Accountability Log
- Healthcare Utilization Form
- Aveir LP Assessment and Programming Form (Follow-Up) with device session print out PDFs
- Adverse Event Form, if applicable
- Device Deficiency Form, if applicable
- Deviation Form, if applicable
- COVID-19 Assessment Log, if applicable

6.4 System Revision without a Replacement Aveir LP

In the event an Aveir LP must be replaced during the follow-up period, investigators may opt to revise the Aveir LP without a replacement Aveir LP in one of the following ways:

- Retrieve the Aveir LP and implant a commercially available pacemaker, CRT device, ICD, or not opt for a replacement device.
- Deactivate the Aveir LP and implant a commercially available pacemaker, CRT device, ICD, or not opt for a replacement device.

Clinical Investigation Plan for Europe

When considering Aveir LP retrieval, investigators will refer to the respective IFUs. Sponsor representatives may also assist the team in equipment setup prior to and during a procedure.

If the subject has all Aveir LPs removed or deactivated at any time during the clinical investigation, and the subject will not receive a replacement Aveir LP, the site will follow the subject for at least 30 days. At the end of the 30 days, the investigator will withdraw the subject. If the subject has at least one active Aveir LP after a system revision procedure, the subject must continue with his/her ongoing follow-up schedule.

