3.3.1 Subject Follow-up in cases of early termination or suspension

Should the Sponsor discontinue the clinical investigation, sites will follow subjects per routine hospital practice with device-related AEs reported to the Sponsor as per vigilance/commercial reporting requirements. The investigator shall return all clinical investigation materials (including

Clinical Investigation Plan for Europe

devices) to the Sponsor and provide a written statement to the IRB/EC (if applicable). All applicable clinical investigation documents shall be subject to the same retention policy as detailed in Section 11.5 of the CIP. A final report will be provided to investigators, competent authorities, and all IRBs/ECs within 3 months of the end of a study in the event of early termination or temporary halt.

If the Sponsor suspends or prematurely terminates the clinical investigation at an individual site in the interest of safety, the Sponsor will inform all other Principal Investigators.

If suspension or premature termination occurs, the Sponsor will remain responsible for providing resources to fulfill the obligations from the CIP and existing agreements for following the subjects enrolled in the clinical investigation, and the Principal Investigator or authorized designee will promptly inform the enrolled subjects at his/her site, if appropriate.

A Principal Investigator, IRB/EC, or regulatory authority may also suspend or prematurely terminate participation in the clinical investigation at the investigational site(s) for which they are responsible. The investigators will follow the requirements specified in the Clinical Trial Agreement.

If a suspended investigation is to be resumed, a prior approval should be obtained from the EC/IRB and a notification should be sent to the regulatory bodies.

4.0 **ENDPOINTS**

The primary and secondary endpoint analyses will be based on newly enrolled (*de novo*) subjects in the investigation who have an attempted implant. *De novo* subjects are defined as subjects that do not have an implanted pacemaker on the date of consent through the date of the Aveir LP implant.

4.1 **Primary Endpoints and Rationale**

4.1.1 **Primary Safety Endpoint**

The primary safety endpoint evaluates the 12-month Aveir DR LP system complication-free-rate in *de novo* subjects based on CEC adjudication of adverse events.

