5.5 Subject Withdrawal and Discontinuation

Each subject meeting all general and screening eligibility criteria shall remain in the clinical investigation until completion of the required follow-up period; however, a subject's participation in any clinical investigation is voluntary and the subject has the right to withdraw at any time without penalty or loss of benefit. Conceivable reasons for discontinuation may include, but are not limited to, the following:

- Subject death
- Subject voluntary withdrawal
- Subject lost-to-follow-up
- Subject's follow-up is terminated according to Section 3.3
- Unsuccessful Implant
- LP explanted and not re-implanted
- LP abandoned and Aveir LP not re-implanted

Sites must notify the Sponsor of the reason(s) for subject discontinuation. Investigators must also report this to their respective IRB/EC as defined by their institution's procedure(s).

No additional follow-up is required or data recorded from subjects once withdrawn from the clinical investigation, except for the status (deceased/alive).

However, if a subject withdraws from the investigation due to problems related to the safety or performance of the device under investigation, the investigator shall ask for the subject's permission to follow his/her status/condition outside of the clinical investigation according to standard of care.

Lost-to-Follow-up

Clinical Investigation Plan for Europe

If the subject misses two consecutive scheduled follow-up time points and the attempts at contacting the subject detailed below are unsuccessful, then the subject is considered lost-to-follow-up. Site personnel shall make all reasonable efforts to locate and communicate with the subject (and document these efforts in the source documents), including the following, at each contact time point:

- A minimum of two telephone calls on different days over the specified follow-up windows to contact the subject should be recorded in the source documentation, including date, time and initials of site personnel trying to make contact.
- If these attempts are unsuccessful, the site should send a certified letter to the subject.
- If a subject misses one or more non-consecutive follow-up contact time points, it will be considered a missed visit. The subject may then return for subsequent visits. If the subject misses two consecutive time points and the above-mentioned attempts at communicating with the subject are unsuccessful, the subject will be considered lost-to-follow-up.

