Sponsor understands that the following items meet the definition of serious adverse event if they require hospitalization or prolong hospitalization, even though an invasive approach may not be necessary to resolve: AV fistula, pseudoaneurysm, blood transfusions, tricuspid valve damage, pericardial effusion, pulmonary embolus, device dislodgement, right ventricular or right atrial perforation, thrombus formation on the device, ventricular arrhythmias even if not associated with an invasive strategy to remedy.

Non-invasive means such as device re-programming do not meet the criteria for medical or surgical intervention.

Successful Implant: A subject who leaves an attempted *de novo* implant procedure with functioning atrial and ventricular LPs implanted, including established i2i communication

Clinical Investigation Plan for Europe

Successful Upgrade: A subject with a pre-existing Aveir ventricular LP who was successfully implanted with an Aveir atrial LP, and the Aveir VR LP can be programmed to a dual-chamber mode

Time to discharge: Defined as the time from introducer sheath removal to discharge.

Unanticipated (serious) adverse device effect (UADE/USADE): Any serious adverse effect on health or safety or any life-threatening problem or death caused by, or associated with, a device, if that effect, problem, or death was not previously identified in nature, severity, or degree of incidence in the investigational plan or application (including a supplementary plan or application), or any other unanticipated serious problem associated with a device that relates to the rights, safety, or welfare of subjects. [21 CFR 812.3(s)]

Unavoidable adverse event: An unavoidable AE is defined as an adverse event related to the implant procedure that is expected to occur for a projected duration in all subjects.

Undersensing: The failure of the pulse generator to sense R-waves, causing delivery of inappropriately timed, asynchronous or competitive output pulses. Undersensing can sometimes be corrected by programming the device to a more sensitive setting, i.e., decreasing the millivolt value.

Unsuccessful Implant: A subject who leaves an attempted *de novo* implant procedure without a functioning atrial or ventricular LP implanted, or where i2i communication was not established.

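### Subjects still event-free when all their leadless pacemakers are deactivated in place are withdrawn after 30 days, so a later device complication cannot reach either 12-month safety endpoint

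*Protocol*

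**What the plan says.** Protocol section 6.4 covers system revision without a replacement Aveir LP. One route it allows is: "Deactivate the Aveir LP and implant a commercially available pacemaker, CRT device, ICD, or not opt for a replacement device". If all Aveir LPs are "removed or deactivated at any time during the clinical investigation" and no replacement Aveir LP is given, "the site will follow the subject for at least 30 days. At the end of the 30 days, the investigator will withdraw the subject". The rule does not separate an empty heart from one that still holds a deactivated device. The same section keeps other subjects in the study: "If the subject has at least one active Aveir LP after a system revision procedure, the subject must continue with his/her ongoing follow-up schedule".

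Section 5.5 lists "LP abandoned and Aveir LP not re-implanted" among the reasons for discontinuation and adds: "No additional follow-up is required or data recorded from subjects once withdrawn from the clinical investigation", apart from whether the subject is alive. Section 7.3.1 ends safety surveillance at withdrawal.

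The endpoint runs longer than this follow-up. In protocol section 4.1.1, "The primary safety endpoint evaluates the 12-month Aveir DR LP system complication-free-rate" in de novo subjects. The secondary safety endpoint is the 12-month rate for the atrial LP. Both are Kaplan-Meier estimates in the full analysis population (SAP sections 2.3.1 and 2.3.4). SAP section 2.2.3 censors subjects without an event at the last time they were known to be event-free, and uses the first event for the others.

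**The concern.** The 30-day rule suits a subject with no device left, and section 6.2.9 uses the same period when no LP was implanted. A deactivated LP is still an implanted investigational device. Protocol Appendix IV lists dislodgement, embolism, thrombosis and endocarditis, and none of these depends on the device pacing. Appendix II counts dislodgement and thrombus on the device as serious when they cause or prolong hospitalization. Section 15.6 says that the risk of dislodgement or migration cannot be estimated with confidence without clinical data, and section 1.1.2 describes the trial as the first in-human evaluation of this system.

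Such a subject need not already be an endpoint event. Appendix II states: "Non-invasive means such as device re-programming do not meet the criteria for medical or surgical intervention". Section 6.4 does not require a replacement device, and it allows deactivation on a change to a CRT device or ICD, which may have nothing to do with the LP.

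Two things are at stake. Safety experience with some retained investigational devices stops short of the endpoint horizon. And the censoring is triggered by abandonment of the device under test, so the Kaplan-Meier assumption that censored subjects carry the same later risk as those remaining is doubtful.

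**Working it through.** **1. Plan's own figure.** The documents state no number of all-deactivated subjects and no number of events after withdrawal, so there is nothing to reproduce on this point. The nearest figure is the 300 subjects for secondary safety (protocol section 8.3: 90% assumed, goal 82%, one-sided 2.5%). A normal approximation gives power of 98.3% (null variance) to 99.6% (Wald). The plan's own power is redacted, so the two cannot be compared.

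**2. Who is affected.**

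| Situation | Result under the plan | Event data lost? |
|---|---|---|
| LP deactivated, new Aveir LP implanted (6.3) | stays on schedule | No |
| One LP deactivated, another active (6.4) | stays on schedule | No |
| All LPs inactive, qualifying SADE already recorded | already a failure; only the first event counts (SAP 2.2.3) | No, for the endpoint |
| All LPs removed, no SADE | 30 days, withdrawn, censored | No device remains |
| All LPs inactive, at least one left in place, no SADE | 30 days, withdrawn, censored | **Yes** |

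**3. Pass limits at N = 300.** These use complete data and the Wald lower bound p − 1.96·√(p(1−p)/300).
- Primary, goal 76.5%: 243/300 = 81.0% gives 0.8100 − 0.0444 = 76.56%, a pass. 242/300 gives about 76.2%, a fail. At most 57 events are allowed.
- Secondary, goal 82%: 258/300 = 86.0% is the smallest passing count. At most 42 events are allowed.

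**4. Size of the bias.** Suppose E events occur early, m event-free subjects are then censored, and L late events occur among the remaining n = 300 − E − m. If a share q of the m subjects would have had a SADE by month 12:
- with censoring: CFR = [(300−E)/300]·(1 − L/n)
- with full follow-up: CFR = [(300−E)/300]·(1 − (L + qm)/(300−E))
- difference = (m/300)·(q − L/n)

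The values of E, L, m and q are assumptions. Take E = 30, L = 1, m = 6, q = 0.5, so n = 264. With censoring, 0.9 × 263/264 = 89.66%. With full follow-up, 0.9 × 266/270 = 88.67%. The difference is 0.99 points.

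| m | q = 0.1 | q = 0.5 | q = 1 |
|---|---|---|---|
| 1 | 0.03 | 0.17 | 0.33 |
| 3 | 0.10 | 0.50 | 1.00 |
| 6 | 0.19 | 0.99 | 1.99 |

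Entries are points of CFR; E = 45 and E = 53 give the same values to two decimals. One recovered SADE is worth about 1/300 = 0.33 points. If q equals the late risk of the remaining subjects (L/n, here 1/264), there is no bias, only lost information.

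**5. Hidden SADEs needed to reverse a pass.**
- Primary: 58 − 54 = 4 at an observed CFR of about 82%; 58 − 46 = 12 at about 84.7%; 58 − 31 = 27 at about 89.7%.
- Secondary at the planned 90% (30 events): 43 − 30 = 13.

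**The case against.** The strongest reply is that few subjects can fall in the gap. Many device-driven revisions will already be failures: Appendix II makes an event serious if it needs an invasive remedy, and hospitalization makes it serious in any case. Section 4.1.1.1 cites leadless experience in which most complications occur within 30 days of implant. SAP section 2.8 summarizes the reasons for missing data and plans a tipping-point analysis for primary safety. Section 5.5 asks investigators to seek permission to follow subjects who withdraw over device safety or performance.

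Most of this stands and limits the size of the point, but it does not close the gap. Section 7.1.2 lacks Appendix II's wording on an invasive remedy, so which subjects already count is not settled. The cited timing is not from this dual-chamber system. The tipping-point details are redacted; the analysis may cover these withdrawals, but it cannot recover events, and none is visible for secondary safety. The follow-up in section 5.5 is outside the investigation, with no stated route to the CEC.

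A reader might infer three stronger things that the documents do not support:
- That nothing is collected on any abandoned LP after 30 days. Sections 6.3 and 6.4 keep subjects with a new or still-active Aveir LP on schedule.
- That every later SADE after deactivation is lost to the endpoint. Under the first-event rule, a subject who already had a SADE contributes nothing further.
- That one event could decide the result. That is true at any fixed threshold and is not particular to this rule.

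**Conclusion.** The point holds for a narrow group: subjects with no active Aveir LP, at least one deactivated LP still in place, and no qualifying SADE at withdrawal. For them a later device-related SADE cannot enter either 12-month safety endpoint. The censoring may be informative; it is less clearly so when deactivation followed an unrelated change of therapy.

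The likely effect is small: about 0.03 to 1.0 points of CFR, assuming 1 to 6 such subjects and a 10% to 50% late SADE risk. The 2-point figure for six subjects requires all six to have a late SADE. A reversal is unlikely unless the observed rate is close to the limit. This is a cheap improvement to safety capture and does not threaten the trial's conclusion.

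**What to change.** For data collection only, with no change to device management:

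1. In protocol section 6.4, keep the 30-day follow-up when all LPs have been removed. When any deactivated LP remains in the body, continue adverse-event collection and CEC adjudication through 12 months.
2. Add wording that expressly permits remote safety contact for these subjects. Section 6.6 now allows a remote assessment only when the subject cannot return despite all efforts, and it treats missed testing as a deviation, so it cannot simply be cited.
3. Align the abandoned-LP item in section 5.5 with section 6.4. The item is not limited to subjects whose LPs are all inactive, so read alone it conflicts with the continuation rule.
4. In the SAP, add a sensitivity analysis of both safety endpoints that counts event-free, all-deactivated withdrawals as failures.
5. Reconcile section 7.1.2 with Appendix II on invasive remedies, since that wording decides who is already an event.

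The cost is protocol and SAP wording, a few extra safety contacts, and possibly a slightly lower CFR. No procedure is added.

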6.4.1 Data Submission

The site will complete and submit the following case report forms to Abbott Medical using the EDC system:

- System Revision Form
- Device Accountability Log
- Healthcare Utilization Form
- Aveir LP Assessment and Programming Form (Follow-Up) with device session print out PDFs
- Study Withdrawal Form, if applicable
- Adverse Event Form, if applicable
- Device Deficiency Form, if applicable
- Deviation Form, if applicable
- COVID-19 Assessment Log, if applicable

6.5 Pre-Discharge (In-hospital)

6.5.1 Access-site Management During Hospital Stay

Investigators will manage vascular-access sites per standard of care for procedures using large bore venous access. Investigators will assess and document any post-procedural access-site bleeding events based on the following grading system.

ACCESS-SITE OOZING: Superficial bleeding of a cutaneous or subcutaneous origin characterized by diffuse localized bleeding and controlled with minimal care (e.g., application of manual pressure, application of sandbag or other pressure dressing as per standard of care).

ACCESS-SITE HEMATOMA: A localized collection of extravasated blood in subcutaneous tissue at the access site that does not require intervention. A metric ruler should be used to measure the widest portion of the hematoma.

ACCESS-SITE HEMATOMA REQUIRING INTERVENTION: A localized collection of extravasated blood in subcutaneous tissue at the access site that requires intervention including wound exploration (e.g., acutely expanding hematoma, acute leg pain/numbness/swelling) and/or prolongation of hospital stay.

Clinical Investigation Plan for Europe

6.5.2 Pre-Discharge Assessment

Investigators will assess all subjects at the implant center prior to hospital discharge, or within 2-days post implant, whichever is shorter. The clinical investigation team will:

- Assess for adverse events and deviations from investigation plan
- Assess for changes in beta blockers, ACE, ARB, anti-coagulants, anti-platelets, anti-arrhythmics
- Measure and record Aveir LP performance, as described in Section 6.2.5 LP Assessment and Programming
- Program Aveir LP per physician discretion
- Obtain a 12-lead ECG with pacing ON
- Obtain a posterior/anterior (P/A) and lateral view chest x-ray to assess final LP position
- Investigator will use medical judgment and provide institutional standard of care for post-pacemaker-implant monitoring

6.5.3 Data Submission

The site will complete and submit the following case report forms and device print outs to Abbott Medical using the EDC system:

- Pre-Discharge Form (includes medication changes)
- Aveir LP Assessment and Programming Form (Follow-Up) with device session print out PDFs
- Healthcare Utilization Form, if applicable
- Adverse Event Form, if applicable
- Device Deficiency Form, if applicable
- Deviation Form, if applicable
- Device Accountability Log, if applicable
- System Revision Form, if applicable
- COVID-19 Assessment Log, if applicable
- Study Withdrawal Form, if applicable

Any post-procedure chest X-ray imaging should be de-identified and submitted to the Sponsor upon Sponsor request.

Clinical Investigation Plan for Europe

6.6 Follow-up Assessments

The site will perform the required clinical follow-up at the following intervals for all subjects implanted with an Aveir DR LP system:

- 1 month (\pm 15 days) follow-up site visit
- 3 month (\pm 30 days) follow-up site visit
- 6 month (\pm 30 days) follow up site visit
- 12 month (\pm 45 days) follow up site visit
- Every 6 months thereafter until study completion (\pm 45 days)

Please refer to Section 13.0 for more details on the conditions of study completion.

Dates for follow-up visits will be calculated from the date of the implant procedure. Follow-up assessments can be performed at any point within the pre-specified follow-up visit window.

Every effort should be made by the site personnel to have the subject return to the investigational site for all follow-up visits. If, despite all efforts, the subject is unable to return to the site during a follow-up window, subjects may undergo a remote follow-up assessment to collect applicable non-device performance data. Remote assessments should include telephone contact with the subject and/or a visit to a medical facility with all data that can be reasonably and legally collected remotely on the study subject. Follow-up visits occurring at non-study sites will be limited to standard of care data collection only. Authorization for the release of medical records from a non-study facility is the responsibility of the investigational site. Any missed testing will be considered a protocol deviation.

An enrolled subject may only be followed at another investigational site with prior agreement from that site's Investigator and from the Sponsor.

6.6.1 1-Month Follow-Up Visit

The 1-month follow-up visit will occur 30 days (\pm 15 days) post-implant procedure and will include the following assessments:

- Assess for adverse events and deviations from investigation plan
- Assess for changes in beta blockers, ACE, ARB, anti-coagulants, anti-platelets, anti-arrhythmics
- Assess Quality of Life (EQ-5D 5L)
- Measure and record LP performance, as described in Section 6.2.5 LP Assessment and Programming
- Program Aveir LP and adjust programmable parameters of LP, as needed

Clinical Investigation Plan for Europe

- **Optional:** 6-Minute Walk Test (6MWT) only for those capable *de novo* subjects who may be appropriately programmed temporarily in AAIR mode and who have a tolerance of high sensor-driven rates²
 - Administer the 6MWT with the rate-response feature in **AAIR ON or Passive** mode using the Rate Response Optimization function of the programmer for the Aveir atrial LP (Refer to the 6MWT protocol in Appendix V).
 - Assess Magnet Mode in **AAIR ON or Passive**
 - After completing the 6MWT, use the Rate Response Optimization function of the programmer to model the response of the algorithm to the 6MWT protocol so that a peak sensor rate of approximately 100 beats/min is achieved. The results of this Rate Response Optimization will be used to adjust programmable sensor parameters of the Aveir atrial LP in preparation for the CAEP protocol to be administered in a subsequent visit.

